8. ETHICAL CONSIDERATIONS
9. STATISTICAL ANALYSIS
10. STUDY COSTS
11. PUBLICATION OF RESULTS
12. SPONSOR ROLE AND RESPONSIBILITY
13. REFERENCES

1. INTRODUCTION

Fibromyalgia is a chronic disorder of uncertain aetiology, characterized by widespread pain, muscle tenderness, and decreased pain threshold to pressure and other stimuli.¹ Its pathophysiology is still elusive, although evidence support a derangement in pain processing and modulation.¹ Clinical manifestations of fibromyalgia encompass a large range of symptoms including fatigue, unrefreshing sleep, cognitive and memory disturbances ("*fibro fog*"), anxiety, depression, chronic headache, gastrointestinal problems and more.¹

Obesity is a well-known aggravating factor for musculoskeletal pain, such as in knee osteoarthritis.² Epidemiological data show that fibromyalgia patients have higher prevalence of obesity (40%) and overweight (30%) and that excess of body weight influences course and activity of fibromyalgia.² Similarly, obesity influences pain and progression of knee osteoarthritis.³

In the last years, a new nutritional approach – namely Very Low Calorie Ketogenic Diet (VLCKD) – has been proposed as a potential therapeutic option in different diseases that shares common clinical and pathophysiological features with fibromyalgia and osteoarthritis.⁴

The core characteristics of the VLCKD are the association of a high amount of fat, with low carbohydrate intake, usually a macronutrient ratio of fat to protein and carbohydrate combined equal to 3–4:1.⁴ The objective is to achieve ketosis, leading to reduced insulin secretion and glycaemia within 48h.⁴ Ketosis is achieved when less than 50 g of carbohydrates per day are introduced, with either restricted or unrestricted fat and calorie intake.⁵

VLCKD have been demonstrated to provide clear clinical benefits in different diseases - in particular refractory epilepsy⁶ - and to achieve rapid weight loss in obese subjects who failed other dietetic interventions.⁷ For their efficacy and safety profile, VLCKD entered as a therapeutic options in recent guidelines for management of obesity.^{8,9}

Furthermore, other studies evaluated the effect of VLCKD on conditions that shares common pathophysiological and clinical background with fibromyalgia. Accumulating evidence suggest positive effects on mood¹⁰, cognitive functions,¹¹ as well as an improvement in nociception¹² and sleep quality.¹³

1.1 Aim of the study

On the basis of this background, aim of this pilot study is to investigate the effects of VLCKD in obese patients with fibromyalgia and symptomatic knee osteoarthritis.

2. STUDY DESIGN AND SETTING

2.1 Study design

Interventional study. Study procedures will be performed in agreement with current clinical practice guidelines^{8,9}.

2.2 Study setting

Rheumatology Outpatient Clinic, Medicine & Rheumatology Unit, IRCCS Istituto Ortopedico Rizzoli, Bologna.

3. PATIENTS

3.1 General characteristics of patients

Adult patients with fibromyalgia or symptomatic knee osteoarthritis and comorbid obesity eligible to VLCKD as defined according to Italian Standards for Treatment of Obesity, released by the Italian Society for the Study of Obesity (SIO) and the Italian Association of Dietetics and Clinical Nutrition (ADI) (2016–2017)⁹ and the recommendations of the Italian Society of Endocrinology (SIE) for VLCKD.⁸

3.2 Inclusion criteria

Age > 18 years and < 65 years
AND
Body mass index ≥ 30 kg/m ²
AND
Failed to achieve weight loss with standard low-calories diet
AND
Any of the following conditions: 
• BMI ≥ 35 kg/m²• Past diagnosis of type 2 diabetes without β-cell failure• Hypertriglyceridemia (fasting triglycerides ≥ 150 mg/dL) or taking lipid-lowering medications• Hypercholesterolemia (total cholesterol > 200 mg/dL) or taking lipid-lowering medications• Past diagnosis of arterial hypertension or taking blood pressure-lowering medications• Past diagnosis of non-alcoholic fatty liver disease• Past diagnosis of heart failure class NYHA I-II• Past history of myocardial infarction (> 12 months), stroke/minor stroke (> 12 months)• Past diagnosis of carotid atherosclerosis• Past diagnosis of polycystic ovary syndrome (PCOS)• Past diagnosis of neurodegenerative disorders
AND
Fibromyalgia classified according to 2016 Revisions to the 2010/2011 European League Against Rheumatism (EULAR)/ American College of Rheumatology (ACR) criteria ¹⁴
OR
Symptomatic knee osteoarthritis classified according to the ACR criteria ¹⁵

3.3 Exclusion criteria

Exclusion criteria have been established on the basis of the abovementioned clinical practice guidelines^{8,9}:

- Age < 18 or > 65 years
- Currently pregnant or breastfeeding
- Past diagnosis of type 1 diabetes mellitus, latent autoimmune diabetes in adults, β -cell failure in type 2 diabetes mellitus, use of sodium/glucose cotransporter 2 (SGLT2) inhibitors (risk for euglycemic diabetic ketoacidosis)
- Past diagnosis of kidney failure and moderate-to-severe chronic kidney disease, liver failure, heart failure NYHA III-IV, respiratory failure
- Past diagnosis of unstable angina
- Recent stroke or myocardial infarction (< 12 months)
- Cardiac arrhythmias
- Past diagnosis of eating disorders and other severe mental illnesses, alcohol and substance abuse
- Active/severe infections
- 48 h prior to elective surgery or invasive procedures and perioperative period
- Past diagnosis of rare disorders: porphyria, carnitine deficiency, carnitine palmitoyltransferase deficiency, carnitine-acylcarnitine translocase deficiency, mitochondrial fatty acid β -oxidation disorders, pyruvate carboxylase deficiency
- Allergy to protein-preparations ingredients
- Past or current history of gallstones

4. DIETETIC INTERVENTION

4.1 Very low-calorie ketogenic diet (VLCKD)

A personalized VLCKD will be prepared for each patient by specialized dietitians at IRCCS Istituto Ortopedico Rizzoli, Bologna using a combination of commercially-available ketogenic preparations and patient's handmade prepared meals (see attachment "VLCKD"). The commercial preparations will be ordered for free by an authorized supplier (see 9) on the basis of individual choices and preferences expressed during nutritional interview, and delivered by the seller to the Dietetic Service – IRCCS Istituto Ortopedico Rizzoli, and subsequently hand-delivered to patients by a dietician investigator.

Briefly, VLCKD is a nutritional intervention that mimics fasting through a marked restriction of daily carbohydrate intake, usually lower than 30 g/day (\approx 13% of total energy intake), with a relative increase in the proportions of fat (\approx 44%) and protein (\approx 43%) and a total daily energy intake < 800 kcal, depending on the amount and quality of protein preparations. Nonetheless, VLCKD should not be considered as a high-protein diet, since its daily protein intake is approximately 1.2–1.5 g/kg of ideal body weight (BMI 22.5 kg/m²).

According to clinical practice guidelines^{8,9}, VLCKD is based on protein preparations of high biological value derived from green peas, eggs, soy and whey. Each protein preparation is composed by approximately 18 g protein, 4 g carbohydrate, 3 g fat (mainly high-oleic vegetable oils) and provides approximately 100–150 kcal. Therefore, VLCKD is characterized by a low lipid content, mainly deriving from olive oil (\approx 20 g per day).

4.2 Weight loss program

The weight-loss program will be preceded by a free-diet phase (Phase 0, duration: 4 weeks), during which the patient will be invited to eat normal meals.

The ketogenic period will be divided in three different phases.

During the first phase (Phase 1, duration: 4 weeks), patients are allowed to eat four to six (depending on ideal body weight) of such protein preparations and low-carbohydrate vegetables. Patients will be instructed to maintain the intake of clear liquids (water, tea, coffee or unsweetened carbonated drinks) > 2 L/day.

In the next phases, the state of ketosis is still maintained, but one (Phase 2, duration: 2 weeks) or two (Phase 3, duration: 2 weeks) of the provided meals (lunch or/and dinner) are gradually replaced by natural protein meals (meat/fish/eggs/legumes).

Following the ketogenic period, carbohydrates are gradually reintroduced, starting from foods with the lowest glycaemic load (fruit, dairy products—Phase 4, duration: 4 weeks), followed by foods with moderate (legumes—Phase 5, duration: 4 weeks) and high glycaemic load (bread, pasta and cereals—Phase 6, duration 4 weeks). The gradual reintroduction of food items allows for a progressive nutritional education that supports long-term weight-loss maintenance.

Nutritional details of each phase are reported in the attachment “VLCKD”.

5. ASSESSMENT OF DISEASE ACTIVITY

5.1 Assessment of fibromyalgia activity

Assessment of disease activity will be performed using validated Italian language self-administered tools (patient-reported outcomes, PROs) as suggested by the OMERACT proposal for Fibromyalgia Responder Index and Disease Activity Score¹⁶, including:

- 1) Fibromyalgia Impact Questionnaire (FIQ)¹⁷
- 2) Short-Form 36 (SF-36)¹⁸
- 3) EuroQoL (EQ-5D)¹⁹
- 4) Hospital Anxiety and Depression Scale (HADS)²⁰

5.2 Assessment of knee osteoarthritis activity

Assessment of disease activity will be performed at weekly intervals using self-administered PROs as suggested by the OARSI Clinical Trials Recommendations: Design and Conduct of Clinical Trials of Rehabilitation Interventions for Osteoarthritis.²¹

1. Western Ontario and McMaster Universities (WOMAC) Osteoarthritis Index²²
2. EuroQoL EQ-5D
3. SF-36.

6. STUDY PROTOCOL

6.1 Study periods

As already mentioned, the study will be conducted following different periods:

1. **Free diet (4 weeks, Phase 0).** After recruitment (T-4), the patient will enter "free diet phase" in which he/she will be asked to follow a normal free diet for 4 weeks. During this period, a nutritional interview will be carried out by a trained dietician who will elaborate a personalized diet and order the ketogenic products on the basis of patient's preferences.
2. **VLCKD (8 weeks, Phases 1-3).** After the free diet period, the patient will start the VLCKD regimen as described (4.1 and "VLCKD" attachment). At the beginning of this period (T0) a box with the commercial products necessary to cover the whole study period will be hand-delivered by a dietician that will instruct the patient on the correct use and storage.
3. **Maintenance (12 weeks, Phases 4-6).** After VLCKD phase, the patient will start maintenance period as described (4.1 and "VLCKD" attachment).

6.2 Timing of disease activity and weight assessment

Study procedures are graphically summarized in the attachment "Study chart".

Patient-reported outcomes described in 5.1 and 5.2 will be obtained at T-4, T0, T1, T2, T3, T4, T5, T6, T7, T8, T12, T16, and T20. Patients will be instructed to fill the questionnaires at appropriate intervals and bring them at the subsequent office visits.

During the office visits (T0, T8, T12, T16, T20), a rheumatologist will perform medical interview with special focus on adverse events and routine musculoskeletal visit; weight and height will be measured and recorded.

6.3 Ketosis assessment

Ketosis assessment will be performed using urine strips (Siemens Multistix 10 sg) provided at time of enrolment (T0) at weekly interval from week T0 to T12. Patients will be instructed on correct usage of the strips and to take a picture of urine stick that will be sent by email to a dedicate address for evaluation.

7. SAFETY MONITORING

7.1 Blood tests

Following the abovementioned clinical guidelines^{8, 9}, safety will be monitored through regular blood and urine tests:

- Before VLCKD and every 4 weeks (T0-T4-T8): complete blood count (CBC), creatinine, blood urea nitrogen (BUN), uric acid, glucose, HbA1c, insulin, total cholesterol, HDL-cholesterol, LDL-cholesterol, triglycerides (serum), ALT, AST, γ -GT, total and direct bilirubin, Sodium, potassium, calcium, magnesium, inorganic phosphate, complete urinalysis and microalbuminuria, 25-hydroxyvitamin D, C-reactive protein
- Before VLCKD and at the end of VLCKD (T0-T8): Body composition by whole body DEXA

7.2 Adverse events monitoring

Adverse events will be systematically monitored during each office visits (see 6.1); any potential adverse event will be reported on CRF. In case of adverse event, the investigator, in agreement with the patient, will decide if continue or withdraw from the study. Furthermore, the patient and his/her general practitioner will be able to communicate to the study staff any suspect adverse events using the phone number reported in patient information sheet.

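### No scheduled adverse-event query falls inside the 8-week ketogenic period, although patients with type 2 diabetes and patients on blood-pressure-lowering drugs can enrol

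*Protocol*

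**What the plan says.** Four parts of the Protocol bear on this point.

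- **Who enters.** Among the alternative qualifying conditions in 3.2 are "Past diagnosis of type 2 diabetes without β-cell failure" and "Past diagnosis of arterial hypertension or taking blood pressure-lowering medications". Section 3.3 excludes type 1 diabetes, latent autoimmune diabetes and β-cell failure. The one glucose-lowering drug class it names is in the exclusion "use of sodium/glucose cotransporter 2 (SGLT2) inhibitors (risk for euglycemic diabetic ketoacidosis".
- **What they receive.** Section 4.1 describes "a total daily energy intake < 800 kcal" with carbohydrate usually under 30 g a day. Sections 4.2 and 6.1 keep patients in the ketogenic phases for 8 weeks. The Introduction describes ketosis as "leading to reduced insulin secretion and glycaemia within 48h".
- **How adverse events are sought.** Section 7.2 says: "Adverse events will be systematically monitored during each office visits (see 6.1". Section 6.1 describes the study periods; the visit list is in 6.2 (T0, T8, T12, T16, T20). At these visits a rheumatologist interviews the patient, with attention to adverse events, and weight and height are taken. Section 7.2 also gives patients and their general practitioners a phone number.
- **What else is scheduled on the diet.** There are blood and urine tests at T4 (7.1), a weekly strip photograph by e-mail from T0 to T12 (6.3), and weekly self-completed questionnaires that patients bring to the next visit (6.2).

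**The concern.** The study deliberately recruits patients whose background drugs may need a lower dose once energy and carbohydrate are cut this far. For glucose, the Protocol itself expects a fall soon after ketosis. For blood pressure, the risk is clinical reasoning; the text does not state it. By excluding SGLT2 inhibitors for a named diet-drug risk, the sponsor shows that it has considered such interactions.

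Followed exactly, however, the visible schedule asks nobody about adverse events while they are on the diet. The first systematic query after T0 comes at T8, when the ketogenic period is over. Two things are at stake. One is patient safety in the weeks when drug doses are most likely to need attention. The other is the quality of the safety data: a mild or transient event that nobody phones in depends on recall over as much as 8 weeks.

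**Working it through.** This is a comparison of schedules; no power or error-rate calculation applies.

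**Inputs.** Phase lengths 4, 2 and 2 weeks (4.2); ketogenic period 8 weeks and maintenance 12 weeks (6.1); office visits T0, T8, T12, T16, T20 (6.2); safety tests T0, T4, T8 (7.1); strip e-mails weekly from T0 to T12 (6.3); planned recruitment 20 + 20 = 40 (9).

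**Step 1: reproduce the Protocol's own figure.** Phases 1 to 3: 4 + 2 + 2 = 8 weeks, as stated in 6.1. Adding maintenance, 8 + 12 = 20, which matches T20, so the T-numbers count weeks from the start of the diet. With T0 as day 0, T4 is 4 × 7 = day 28 and T8 is 8 × 7 = day 56.

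**Step 2: visits inside the diet.** Of T0, T8, T12, T16 and T20, the number strictly between T0 and T8 is 0. Because 7.2 ties systematic monitoring to visits, the number of scheduled adverse-event queries in that interval is also 0.

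**Step 3: whether another contact fills the gap.**

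| Contact | Timing strictly between T0 and T8 | Described purpose | Replaces a query? |
|---|---|---|---|
| Blood and urine tests (7.1) | T4, day 28 | Laboratory safety, including glucose, creatinine and electrolytes | In part: no interview is attached |
| Strip e-mail (6.3) | T1 to T7 | Ketosis | No |
| Questionnaires (5.1, 5.2, 6.2) | Completed T1 to T7, handed in at T8 | Disease activity and quality of life | No |
| Phone line (7.2) | Any time | Suspected adverse events | No: unscheduled, and someone must first recognise a problem |

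**Step 4: what a weekly query would change.** E-mails at T1 to T7 number 7. The first is at 1 × 7 = day 7, which is 56 − 7 = 49 days before T8. The longest interval between scheduled queries during the diet falls from 56 to 7 days. The ceiling on workload is 7 × 40 = 280 queries.

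**Not computable.** The Protocol does not say how many patients will be taking glucose- or blood-pressure-lowering drugs. The number could be anything from 0 to 40, so no expected count of events can be given.

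**The case against.** The strongest reply is that much may be covered elsewhere. The Study chart and VLCKD attachments, the case report form and the patient information sheet are not shown. Section 4.2 says "Nutritional details of each phase are reported in the attachment", and 2.1 says "Study procedures will be performed in agreement with current clinical practice guidelines". A rheumatologist interviews the patient at T0, after a 4-week run-in that includes a dietician's interview, so there is time for a drug review. Several higher-risk groups are excluded: β-cell failure, moderate-to-severe kidney disease, NYHA III-IV heart failure and arrhythmias. The T4 panel is broad, and the phone line is open to the general practitioner too.

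Part of this stands. A reader might infer that blood pressure is never measured and that doses are never reviewed. The documents do not support that. The supplied text is silent on both, but the unseen material may provide them, and 6.2 does not say that weight and height are the only measurements.

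A reader might also count from the 48-hour statement in the Introduction and arrive at delays of 28 − 2 = 26 days to the T4 bloods and 56 − 2 = 54 days to the T8 query. That does not hold either. The Introduction does not settle whether the 48 hours run from the start of the diet or from ketosis. It speaks of reduced glycaemia, which is not hypoglycaemia, and calendar gaps do not measure risk.

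The reply does not remove the main point. The visit list in 6.2 and the rule in 7.2 are explicit. If an attachment adds a query between T0 and T8, these sections still need to agree with it.

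**Conclusion.** The point holds for the adverse-event query. On the visible text there are no scheduled queries strictly between T0 and T8, and the first one after T0 is at day 56. It would be too strong to call the diet unmonitored: laboratory tests are due at day 28 and a phone route exists. Neither asks every patient how they are.

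The conclusion assumes that the T-numbers are weeks from the start of the diet (checked above) and that no unseen attachment adds a query. That some enrolled patients with diabetes take glucose-lowering drugs is inferred from the eligibility rules; the Protocol does not state it. The absence of written blood pressure readings and of a written dose decision is a secondary point, conditional on the attachments. The cross-reference from 7.2 to 6.1 is simply wrong, since the visits are in 6.2.

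This should be changed, with medium confidence, because the size of the group at risk is unknown.

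**What to change.** 1. **In 6.3 and 7.2**, add a short adverse-event query to the existing strip e-mail at T1 to T7. For patients on glucose- or blood-pressure-lowering drugs, include symptoms of hypoglycaemia and hypotension. The staff who already evaluate the strip photographs read the replies and pass them to the study physician.
2. **Unless an attachment already provides it**, record glucose- and blood-pressure-lowering drugs and any dose decision at the T0 interview, and take blood pressure at the existing office visits. If an attachment does provide it, say so in 6.2 or 7.1.
3. **In 7.2**, change the cross-reference from 6.1 to 6.2.

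The cost is a small amendment with no new visits: at most 7 short queries per patient (280 in all) and the time to read them. The conditional items add one drug-and-dose entry per patient and five pressure readings (5 × 40 = 200).

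The limits should be stated. No glucose test is added before T4, so symptom-free lows would still be missed. Pressure at the office visits gives T0 and T8 but nothing between. A reading at the T4 blood draw would be welcome, but the text does not say where that blood is drawn, so a day-28 reading for every patient cannot be promised.

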7.3 Women of childbearing age

In women of childbearing age, rapid pregnancy test will be obtained before ketogenic phase to exclude unacknowledged pregnancy. Patients will be instructed to immediately communicate to the study staff the event of unexpected pregnancy during ketogenic phase and to stop immediately the ketogenic diet. In this case, patient will be withdrawn from the study and referred for pregnancy nutritional consultation. No actions will be needed in case of pregnancy of a male patient's partner.

7.4 Insurance

Possible damages arising from participating in the present study will be covered by a study-specific insurance provided by IRCSS Istituto Ortopedico Rizzoli.

8. ETHICAL CONSIDERATIONS

Written informed consent will be obtained by all patients at recruitment. Study procedures will be performed according to the Declaration of Helsinki and clinical practice guidelines^{8, 9}.

9. STATISTICAL ANALYSIS

Given the exploratory nature of the study, an arbitrary number of 20 fibromyalgia and 20 symptomatic knee osteoarthritis patients will be recruited from Rheumatology Outpatient Clinic – IRCCS Istituto Ortopedico Rizzoli, Bologna, Italy. Patients' associations will be involved for volunteer engagement.

Primary measures of efficacy (change in FIQ total score and WOMAC total score, for fibromyalgia and osteoarthritis, respectively) will be compared using paired-sample Student's T tests at time T-4, T0, T8, T20. Analysis of covariance (ANCOVA) will be used to evaluate the effect of baseline disease severity and BMI on change in primary efficacy measures.

Furthermore, other exploratory analyses will be performed:

- Change in secondary outcome measures at T-4, T0, T8, T20;
- Correlation between change in body weight ($\Delta\text{weight}_{T0-T8}$) and change in primary (ΔFIQ_{T0-T8} or $\Delta\text{WOMAC}_{T0-T8}$) and secondary outcome measures;
- Time course of %change in FIQ total score and WOMAC total score from T-4 to T20;
- Student's T test for difference in ΔFIQ_{T0-T8} or $\Delta\text{WOMAC}_{T0-T8}$ in patients who achieved and maintained ketosis during the ketogenic phase (urinary ketones > +5 from week 1 to week 8) vs patient who did not maintained ketosis.

Both per-protocol (PP) and intention-to-treat (ITT) analyses will be performed.

All analyses will be performed using the Statistical Software for Social Sciences (SPSS, IBM) version 23.

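### Section 9 fixes separate paired t-tests while promising ITT; unless scores are imputed, T20 improvement is overstated if patients with poorer observed scores leave more often

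*Protocol*

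**What the plan says.** Protocol section 9 defines the endpoints as "Primary measures of efficacy (change in FIQ total score and WOMAC total score, for fibromyalgia and osteoarthritis, respectively") and compares them by paired "T tests at time T-4, T0, T8, T20". It sets the sample as "an arbitrary number of 20 fibromyalgia and 20 symptomatic knee osteoarthritis patients will be recruited" and adds: "Both per-protocol (PP) and intention-to-treat (ITT) analyses will be performed". ANCOVA is planned to study baseline severity and BMI, and is not described as a way of handling missing scores. A time course of percentage change from T-4 to T20 is listed among the other exploratory analyses.

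Section 6.2 says that the questionnaires "will be obtained at T-4, T0, T1, T2, T3, T4, T5, T6, T7, T8, T12, T16, and T20". That is 13 occasions, of which the primary tests use 4. Patients fill in the forms themselves and bring them to the next office visit; the listed visits are T0, T8, T12, T16 and T20.

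Scores can be lost. After an adverse event, "the investigator, in agreement with the patient, will decide if continue or withdraw from the study" (section 7.2); section 7.3 requires withdrawal on pregnancy. T20 falls 12 weeks after the ketogenic period ends (section 6.1). No dropout rate is given.

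**The concern.** The named estimator and the stated aim pull apart within one section. ITT is meant to speak for everyone who entered. Separate paired t-tests, applied to the scores as they stand, speak for whoever has both scores in each comparison. Once someone leaves between T8 and T20, the T0-T8 and T0-T20 tests rest on different patients. A patient with T8, T12 and T16 scores but no T20 score vanishes from the T0-T20 test, although those three scores show how the patient was doing.

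At stake is the T20 contrast, the latest of the four time points tested and the one that bears on whether a benefit outlasts the ketogenic phase. There is no control group, so little else in the design would reveal that a favourable T20 mean came from selective attendance. With 20 patients per cohort, four losses already make up 20%.

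**Working it through.** The protocol states no power, SD, effect size or dropout rate, so there is no figure of its own to reproduce. The check asks how far the complete-pair mean at T20 moves under stated assumptions.

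**From the protocol:** 20 patients per cohort; paired t-tests at T-4, T0, T8 and T20; scores also due at T4, T12 and T16.

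**Assumed:** normal scores, the correlations, the amount of loss, and what drives it.

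**1. By hand, extreme case.** Let the improvements from T0 at T8 and at T20 each have SD 1 and correlation ρ. If leaving depends only on the T8 change,

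bias at T20 = ρ × (mean T8 change of stayers − mean T8 change of all).

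Suppose that the 4 worst T8 responders of 20 leave (20%). The mean of the upper 16 of 20 standard normal values is 0.333.
- ρ = 0.5: 0.5 × 0.333 = 0.17 SD
- ρ = 0.7: 0.7 × 0.333 = 0.23 SD

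If 4 leave at random, the bracket averages zero and so does the bias.

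**2. Two-time-point simulation** (n = 20, 4,000 runs per setting, true T8 improvement 0.5 SD, true T20 improvement 0 or 0.5 SD, ρ = 0.5 or 0.7). Overstatement at T20 by complete pairs, in SD of change:

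| Loss after T8 | Random | Poor T8 responders more likely to leave | Worst T8 responders all leave |
|---|---|---|---|
| 10% | 0.00 | 0.04-0.07 | 0.09-0.13 |
| 20% | 0.00 | 0.10-0.13 | 0.16-0.24 |
| 30% | 0.00 | 0.14-0.20 | 0.24-0.34 |
| 40% | 0.00 | 0.19-0.28 | 0.31-0.44 |

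The last column agrees with step 1. An estimate that also uses the T8 scores of leavers (regress T20 change on T8 change, evaluate at the mean T8 change of all patients) stayed within about 0.01 SD of the truth throughout. With no true T20 effect and 20% loss, the chance of a falsely significant improvement, nominally 2.5%, was 6-8% under graded loss and 11-17% when the worst responders all left.

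**3. Six-visit simulation** (400 runs per setting; T-4, T0, T8, T12, T16, T20; true T20 change −0.5 SD; dropout graded on the last observed change; 22-27% missing at T20). The paired t-test overstated improvement by 0.07-0.23 SD, that is 14-45% of the true 0.5 SD, and coverage of its 95% interval fell to as low as 87%. A mixed model stayed within 0.06 SD. With random loss of 16-17%, neither was biased.

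**4. Seven 4-weekly visits** (T-4 to T20; 33-34% response-related loss by T20). Paired t-test: 0.23-0.26 SD, coverage 87-89%. Mixed model: at most 0.03 SD, coverage 95-96%. Under random loss, neither was biased. When dropout depended on the unseen score, the mixed model still overstated improvement by 0.10-0.15 SD.

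Steps 2 and 3 use different scales (SD of change, SD of a single score), so the agreement is one of direction and order of magnitude.

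**5. Covariance.** An unstructured matrix has 13 × 14 / 2 = 91 parameters for all 13 occasions and 7 × 8 / 2 = 28 for the seven 4-weekly ones. Both are too many for 20 patients, so a structured covariance is needed.

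**The case against.** - **The protocol never says complete pairs.** This stands. A reader might infer that section 9 commits to dropping incomplete patients. It does not: a paired t-test after imputation keeps all 20, and an imputation rule or a definition of the ITT set may sit in a SAP that is not shown. The absence of either is not the point here. The point is that the estimator named in section 9 gives an ITT answer only if something else is added.
- **The other scores are used.** Partly so: the exploratory time course draws on them. It does not change the T0-T20 comparison.
- **T8 is affected as well.** A reader might infer this, but no T8 bias was calculated. The T1-T7 forms are normally handed in at the T8 visit, so someone who leaves before T8 would often leave few scores behind for any model to use.
- **The mechanism in the calculations suits the remedy.** Fair. Dropout in steps 2 and 3 depends on observed scores, where a mixed model is valid. A further six-visit simulation (300 runs per setting, 29-35% missing, dropout on the unseen current score) gave 0.22-0.35 SD for paired tests and 0.08-0.15 SD for the model: smaller, not zero.
- **This is an exploratory pilot of arbitrary size, and the change scores that section 9 names explicitly run from T0 to T8.** This lowers the stakes. The protocol nowhere designates T20 as its statement on durability. But T20 is among the primary time points, and publication is planned (section 11).

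**Conclusion.** The point holds in conditional form. Section 9 fixes separate paired t-tests for the primary FIQ and WOMAC comparisons and promises ITT. Without imputation, the T0-T20 test uses only patients with both scores and sets aside the intermediate scores of those who leave. If poorer observed scores make leaving more likely, T20 improvement is overstated by about 0.07-0.26 SD at an assumed 20-35% loss. The extreme case, in which the worst responders all leave, reaches 0.34 SD at 30% loss. Random loss gives no bias.

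Dropout rates, correlations and mechanism are all assumptions, so the documents do not support saying that the T20 result will be overstated, only that the chosen test offers no protection if loss is related to response. The direction is the same in every response-related scenario examined. The change is worth making before analysis, at the level of a recommended improvement to an exploratory study.

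**What to change.** Rewrite one paragraph of section 9.

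- **ITT analysis:** one linear mixed model per cohort on the equally spaced 4-weekly totals (T-4, T0, T4, T8, T12, T16, T20), for all patients with a T0 score. Use visit as a categorical fixed effect, a random intercept plus AR(1) errors, and small-sample degrees of freedom. Report the T8-T0 and T20-T0 contrasts with 95% confidence intervals.
- **If the weekly scores are added:** use a covariance based on actual time. Spacing changes from weekly to 4-weekly after T8, and AR(1) by visit order would treat the gaps as equal.
- **Completer analysis:** keep the paired t-tests under that name.
- **Sensitivity analysis:** add a simple one for non-random dropout, for example shifting missing T20 scores towards the T0 value.

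Cost: one paragraph and one model per cohort in the software already named, with no extra visits, patients or data. Downsides: a covariance structure must be chosen in advance, missingness is assumed to depend on observed scores, forms never handed in cannot be recovered, and bias is reduced but not removed if dropout depends on unseen scores.
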